**Low Intensity Focused Ultrasound of Medial Temporal Lobe
Regions for the Improvement of Learning and Memory /
Low Intensity Focused Ultrasound as a Non-Invasive Neural
Prosthetic for the Improvement of Emotion Regulation**

NCT03717922
Document Date: 12/8/2023

APPROACH

Participants. Participants will consist of 21 adults aged 35-90

Subject Recruitment. Participants will be recruited from the Human Connectome Project – Aging participant pool and through fliers placed around campus and greater Los Angeles.

Eligibility. Inclusion criteria: 1) age 35-90, 2) right handed, 3) English dominant language.

Exclusion criteria: contraindications for MRI (e.g. metal implants, pregnancy), history of head injury sufficient to warrant medical attention, history of alcohol or substance abuse or dependence, history of major psychiatric illness requiring treatment, history of cancer or other neoplastic syndromes, history of major neurologic illness (e.g. epilepsy).

Procedures.

Crossover Design. This study will be conducted using a crossover design in which each participant will complete two visits spaced two weeks apart. At one visit, they will receive LIFUP sonication to the right amygdala, and at the other, they will receive sonication to the left entorhinal cortex. The order of conditions will be randomized and counterbalanced across participants. Participants will be blinded to condition order, and all other testing will be conducted the same at both visits.

Screening. Participants who have consented to be contacted regarding future research projects will be contacted by study staff who will conduct a telephone screening to ensure eligibility.

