fMRI and LIFUP administration. Prior to receiving LIFUP sonication, the LIFUP transducer will be aimed at the appropriate target region for the visit (either the amygdala or the entorhinal cortex) and gently strapped in place to their head. Participants will then return to the scanner where a T1 image will verify the position of the LIFUP transducer and allow for estimation of the spatial location of the sonication beam focus. If needed, adjustments to transducer placement will be made to ensure that the beam focus is correctly aimed; an additional T1 will be collected after adjustment. Once correct placement of the transducer has been confirmed, LIFUP will be administered in 10 sonifications at 650kHz, 720mW/cm, duty cycle 5% duration 30s, with 30s spacing between sonifications. LIFUP will be administered with a pulse repetition frequency of 10Hz for amygdala sonication and 100Hz for entorhinal cortex sonication. BOLD fMRI will be collected simultaneously during LIFUP administration.

MRI Data Acquisition. We will use a 3-Tesla Siemens PRISMA scanner. We will collect T1, T2, hi-res hippocampal T2, and diffusion-weighted structural images for each participant.

Additionally, we will collect arterial spin labeling and BOLD fMRI both before and after LIFUP, as well as BOLD fMRI during LIFUP administration. We will be using Human Connectome Project scan sequences to collect these images; detailed information about the protocols can be obtained here: <http://www.humanconnectome.org/documentation/Q1/imaging-protocols.html>.

Behavioral Testing. Participants will be administered the behavioral tests described below twice at each of their in-person sessions; once before LIFUP and once after LIFUP.

Verbal Free Recall Task. Verbal memory will be assessed using the Rey Auditory Verbal Learning Test (RAVLT) which involves repeated presentation of a list of 15 words. The order of RAVLT form administration will be randomized and counterbalanced across participants.

Spatial Navigation Memory Task. Participants will be presented with a computerized spatial arena simulating a museum art gallery. They will be instructed to learn the locations of three objects placed throughout the gallery. After the Learning Phase, the subjects will then be asked to locate the objects' shown location sans stimuli immediately after learning the set of locations of each object. After each learning phase, participants will complete an unrelated Distractor Task

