motion artifacts (using framewise displacement calculations, DVARS and within-subject independent component analysis), scrubbing, slice timing, unwarping and spatial smoothing (Gaussian Kernel FWHM = 8mm). Functional data will be linearly registered to stereotaxic MNI space and co-registered with anatomic data for each participant. Processing of diffusion imaging will include correction for motion, eddy distortion and susceptibility induced distortion and then fitting diffusion tensors to the data, Subjects with greater than 3mm mean displacement will be excluded from analyses. Structural data (T1 and DTI) will be linearly registered to the standard MNI152 T1 2mm brain.

Stimulation-related fMRI Analysis. BOLD fMRI will be collected continuously during the LIFUP paradigms. A block-design model will be used to statistically compare the BOLD signal during LIFUP stimulation blocks to the BOLD signal during no-stimulation blocks. To examine effect of stimulation to target ROI activity, we will extract average BOLD response rates in both the targeted and control (non-targeted) region for each of the blocks and use mixed-effect models to compare activity during LIFUP conditions (on / off) within each ROI. To examine LIFUP-related network connectivity, we will use a seed-based approach and examine whole brain connectivity with the LIFUP target of interest and compare between stimulation (on-off) conditions using psychophysiological interaction modeling (PPI). To assess changes in connectivity in relationship to LIFUP, we will use dynamic connectivity to evaluate changes in ROI across each LIFUP condition. Finally, dynamic causal modeling will allow us to assess and compare how changes in activation in the LIFUP target may causally affect activation in other regions (e.g. increased amygdala activation leads to increased DLPFC activity).

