RS-fMRI. We will compare the functional connectivity of the brain at rest before and after stimulation. Independent component analyses (ICA) will be used to statistically extract functional networks from each participant's rs-fMRI. Dual-regression analysis will then compare resting state networks between baseline and post-LIFUP to determine the effect of LIFUP on resting state functional connectivity. Age, sex and education will be included as additional regressors. Dual regression will also assess the association between these LIFUP-related longitudinal resting state network changes and emotional reactivity and memory performance.

Arterial Spin Labeling. Pulsed Arterial Spin Labeling (PASL) scans produce a perfusion image with voxel values representing local perfusion rates. For each subject, will be collected both before and after LIFUP. These PASL images will then be linearly registered to each subject's T1 structural image. Perfusion images will be processed by using the BASIL (Chappell et al., 2008) toolbox, including partial volume correction, then transferred to MNI space using non-linear registration in FSL. Then, a comparison of pre-vs-post tFUS sonication perfusion in the amygdala and entorhinal cortex will be conducted individually for each subject by subtracting the registered pre- sonication perfusion map from the post-sonication perfusion map. A 2×2 repeated measures analysis of variance (ANOVA), corrected for multiple comparisons using False Discovery Rate (FDR), will then be used to compare the longitudinal perfusion changes between amygdala sonication and ErC sonication.

Hypothesis 2. LIFUP of the amygdala will result in reduced subjective emotional reactivity to emotionally-salient stimuli compared to those presented before LIFUP; this reduction will not be observed with entorhinal cortex LIFUP.

Behavioral Analysis. Subjects, who will be unaware of the exact timing of the sonication onset, will be asked to report any unusual feelings, sensations or distress. To determine the effect of LIFUP on emotional reactivity, analyses of variance (ANOVA) will compare subjective valence

and arousal ratings between pre-LIFUP and post-LIFUP administrations of the IAPS task. Additionally, state and trait anxiety scores will be compared pre and post-LIFUP to determine LIFUP-related changes in anxiety levels.

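### The on/off BOLD analysis tests the target and one unnamed control region separately; if that control is the other visit's target, it cannot separate target engagement from same-side spill or local interference

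*Combined protocol and SAP*

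**What the plan says.** Crossover Design sets the two visits: at one, "they will receive LIFUP sonication to the right amygdala, and at the other, they will receive sonication to the left entorhinal cortex". There is no sham visit. Under fMRI and LIFUP administration, each visit delivers "10 sonifications at 650kHz, 720mW/cm, duty cycle 5% duration 30s, with 30s spacing between sonifications", with a "pulse repetition frequency of 10Hz for amygdala sonication and 100Hz for entorhinal cortex sonication". Before sonication, "a T1 image will verify the position of the LIFUP transducer and allow for estimation of the spatial location of the sonication beam focus"; the transducer is moved if needed and the scan repeated.

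Stimulation-related fMRI Analysis plans to "extract average BOLD response rates in both the targeted and control (non-targeted) region for each of the blocks" and to "use mixed-effect models to compare activity during LIFUP conditions (on / off) within each ROI". It neither names the control region nor gives its side. It states no contrast between regions, or between visits for the same region. MRI Analysis smooths these data with an 8 mm FWHM kernel and applies a 0.01 Hz high-pass filter.

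Hypotheses 1a and 1b predict that the changes follow sonication of one target and not of the other. On sensation, the Behavioral Analysis under Hypothesis 2 describes "Subjects, who will be unaware of the exact timing of the sonication onset" and asks them to report unusual feelings. It does not say how those reports enter any BOLD analysis.

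**The concern.** Hypotheses 1a and 1b are claims of specificity: the sonicated structure responds because it was sonicated. In the ON/OFF data, the control region is what would support that claim. It can do so only if it would respond when the target's signal changes for some other reason.

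Three other causes could follow the same ON/OFF blocks: energy reaching the medial temporal structure next to the target, device interference in voxels near the transducer, and sound or vibration that the participant perceives. The first two act on the sonicated side. A control in the other hemisphere would be unaffected by them, and the result would look like target engagement. What is at stake is whether a positive result supports a statement about the amygdala or the entorhinal cortex, or only about the medial temporal region on that side.

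**Working it through.** The plan gives no figure to reproduce: it states 21 participants but no alpha, power, effect size or SD. The check is mainly a comparison of what each cause would produce.

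**1. Where the control lies.** There are two targets, right amygdala and left entorhinal cortex. Hypotheses 1a and 1b use each as the comparator for the other. If the control is the other visit's target, it is contralateral to the target at both visits. This is an inference; the plan does not say so.

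**2. Whether the planned processing removes block-locked artefact.** Blocks are 30 s on and 30 s off, a 60 s cycle, so the frequency is 1/60 = 0.0167 Hz. That is above the 0.01 Hz cutoff, so anything locked to the blocks passes the filter, as the intended effect must.

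**3. Whether smoothing mixes neighbours.** The relative weight of a Gaussian kernel at distance d is exp(−d²/(2s²)), with s = 8/2.3548 = 3.40 mm. This gives 0.50 at 4 mm, 0.21 at 6 mm, 0.06 at 8 mm and 0.002 at 12 mm. Signal from an immediate neighbour enters the target region; signal from the other hemisphere does not.

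**4. What each cause would show** (step 1 reading of the control):

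| Cause of the ON response | Target ON/OFF | Control ON/OFF |
|---|---|---|
| True target engagement | changes | no change |
| Same-side spill or local interference | changes | no change |
| Sensory response shared across regions | changes | changes |

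The first two rows cannot be told apart. The third can, but only if a contrast uses the information.

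**5. Illustration on assumed effect sizes.** Take a one-sample t test on per-person ON−OFF contrasts, n = 21, df = 20, two-sided 0.05 (critical value 2.086), SD 1 and independent regions. The noncentrality is d√21. There is no true target effect.

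- Local artefact of 0.5 SD in the target: 0.5 × 4.583 = 2.291, giving 59% significant for the target and 5% for the control. For target minus control, d = 0.5/√2 = 0.354, noncentrality 1.620, giving 34%.
- Local artefact of 0.3 SD: noncentrality 1.375, giving 26% for the target. For target minus control, d = 0.212, noncentrality 0.972, giving 15%.
- Shared response of 0.5 SD in all regions and both visits: 59% for the target and 59% for the control. Target minus control, and the same region across visits, both return to 5%.

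A simulation of 20,000 runs at 0.5 SD agrees: 60%, 5% and 34% for the local case; 59%, 59% and 5% for the shared case. In the local case the same-region, cross-visit contrast is also significant in 34% of runs.

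So the missing contrasts would deal with a response shared equally by all regions. They would not deal with a local artefact; that needs a region on the sonicated side.

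**The case against.** The strongest case against this has five parts.

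- **The control is not stated to be contralateral.** This stands. The analysis sections name the amygdala and entorhinal cortex without a side. If the control region is ipsilateral or bilateral, the neighbour is wholly or partly covered already. The documented gap is that the region is undefined.
- **A sensory response would show in the control.** This stands for a response shared across regions. A reader might infer that the control says nothing about sensing; the documents do not support that. The check is incomplete, though. No contrast uses it, the pulse repetition frequency differs between targets (10 against 100 Hz) so sensation may differ by visit, and a sensory response need not reach a medial temporal control. Sensation reports are collected, but not tied to the BOLD data.
- **Beam position is verified.** The T1 check and re-aiming make gross mistargeting less likely, so a reader should not conclude that the wrong structure is probably being sonicated. The scan estimates the focus; it does not measure energy in neighbouring tissue or device effects on BOLD.
- **The predicted directions are opposite.** Hypothesis 1a predicts a BOLD decrease and 1b an increase, so an artefact of one sign cannot support both. This limits the harm. Either hypothesis could still be claimed alone.
- **Other evidence exists.** Perfusion and resting connectivity are measured before and after LIFUP, outside the ON blocks, so interference during sonication cannot produce those changes. Spill that truly modulates the neighbour could. Whole-brain PPI is seeded on the target and is not a test for local artefact.

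A reader might also want a rule that the target must exceed its neighbour, or an adjustment for the sensory response. Neither is safe here: with 8 mm smoothing and predicted change in connected regions, both could remove a real effect.

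**Conclusion.** The point holds in a limited form. On the natural reading of the control region, the planned within-region tests cannot separate target engagement from same-side spill or local interference, and they address sensing only in part. No named adjacent region, sham condition or other planned analysis fills this gap.

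The conclusion rests on one inference, that the control is the other visit's target. If the sponsor meant another region, the plan still has to name it. The 26% and 59% rates (15% and 34% for target minus control) illustrate assumed artefacts of 0.3 and 0.5 SD; they are not estimates for this trial. A reader might infer that such artefacts are present or likely; nothing in the documents shows that. What is shown is that the analysis would not reveal local ones.

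**What to change.** 1. Name the control region and its side.
2. From the same BOLD runs, also extract the same-side neighbour (right entorhinal cortex at the amygdala visit, left amygdala at the entorhinal visit) and auditory and face somatosensory cortex.
3. In the mixed model, test region-by-on/off and target-by-on/off contrasts, and do not rely on separate within-region tests.
4. Report the ON/OFF effects in the neighbour and sensory regions, with confidence intervals, beside the target effect. Do not use them as a pass/fail gate or as covariates.
5. Where target and neighbour cannot be distinguished, limit the conclusion to a medial temporal response on the sonicated side. Where the sensory regions or sensation reports suggest perception, do not state that participants were unaware of sonication.

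No new scans are needed. The cost is a few more region extractions and contrasts, and a more cautious specificity claim. Because of smoothing and true spread to connected regions, some genuine target effects will be described only at the level of the medial temporal region.

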International Affective Picture Stimuli Task. In this task, participants complete multiple trials in which a 15-second fixation cross is followed by a 2-second color-coded instruction for one of three trial types: WATCH (passively view a negative image), VIEW (passively view a neutral image), or REAPPRAISE (actively reappraise a negative image). The instruction image is followed by a 5 second presentation of a negatively or neutrally-valenced image. After each image presentation, participants rate their subjective level of current arousal and the degree of awfulness of the image (valence). The task consists of 24 VIEW trials, 24 WATCH trials, and 48 REAPPRAISE trials. Objective reactivity to each stimulus will be measured using galvanic skin response and heart rate. Emotional reactivity in this task will be quantified using the difference between negative and neutral stimuli (N-S). Emotional reappraisal will be quantified by taking the difference of the negative reappraisal stimuli and the negative stimuli (NR - N).

Data Analysis Plan.

Hypothesis 1a. LIFUP of the amygdala will decrease BOLD activation in the amygdala and functionally associated regions (e.g. DLPFC), as well as functional connectivity between the amygdala and connected regions. It will also increase perfusion in the amygdala. These changes will not be observed in response to LIFUP of the entorhinal cortex.

Hypothesis 1b. LIFUP of the entorhinal cortex will increase BOLD activation in the entorhinal cortex and functionally associated regions (e.g. DLPFC), as well as functional connectivity between the entorhinal cortex and connected regions. It will also increase perfusion in the entorhinal cortex. These changes will not be observed in response to LIFUP of the amygdala.

MRI Analysis. Analyses will be performed using FSL Version 5.0 (www.fmrib.ox.ac.uk/fsl). Stimulation-related functional data processing will include motion correction to the mean image, spatial smoothing (Gaussian Kernel FWHM = 8mm), high-pass temporal filtering ($t > 0.01$ Hz) and regression-based removal of outliers. Processing of rs-fMRI will include correcting for

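### Hypotheses 1a and 1b claim target specificity, but no between-target contrast is specified for ROI BOLD, PPI or resting-state connectivity

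*Combined protocol and SAP*

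**What the plan says.** Hypothesis 1a predicts decreased BOLD activation and connectivity, and increased perfusion, under amygdala sonication, and adds: "These changes will not be observed in response to LIFUP of the entorhinal cortex". Hypothesis 1b predicts increases in all three under entorhinal sonication, and adds: "These changes will not be observed in response to LIFUP of the amygdala".

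The planned contrasts for these measures are:

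- **ROI BOLD** (Stimulation-related fMRI Analysis): the plan will "extract average BOLD response rates in both the targeted and control (non-targeted) region for each of the blocks" and then "use mixed-effect models to compare activity during LIFUP conditions (on / off) within each ROI".
- **PPI** (same section): "examine whole brain connectivity with the LIFUP target of interest and compare between stimulation (on-off) conditions". It does not say whether both seeds are used at both visits.
- **Dynamic connectivity** (same section): "use dynamic connectivity to evaluate changes in ROI across each LIFUP condition". This is ambiguous, because a condition is a sonication target under Crossover Design but on or off in this section.
- **Resting state** (RS-fMRI): "Dual-regression analysis will then compare resting state networks between baseline and post-LIFUP", with age, sex and education as regressors.
- **Perfusion** (Arterial Spin Labeling): a 2×2 repeated-measures ANOVA to "compare the longitudinal perfusion changes between amygdala sonication and ErC sonication".

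Outside Hypothesis 1, the interbeat-interval model under Physiological Analysis lists target as a factor.

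**The concern.** A claim that an effect occurs under one sonication and not under the other is a claim about the difference between the two. Separate on/off or pre/post tests do not estimate that difference. If they are all that is run, the specificity clause can be supported only by a significant result at one visit and a non-significant result at the other.

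A response common to both sonications can produce that pattern by chance. For on/off data the obvious candidate is sensation or arousal from the device; participants' not knowing the exact onset reduces this but does not remove it. For pre/post resting-state data, time in the scanner is a further candidate. A common decrease would favour Hypothesis 1a and a common increase Hypothesis 1b. With 21 participants, a non-significant control visit is also weak evidence that nothing happened there.

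**Working it through.** **Which contrasts include the target.** For three Hypothesis 1 measures (ROI BOLD, PPI, resting state) the text names no target factor, no target interaction and no between-visit comparison. For dynamic connectivity the wording is unclear. For perfusion the between-target comparison is explicit. The plan gives no alpha, power, effect size or SD, so it has no figure of its own to reproduce.

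**Inputs for the illustration.** From the plan: n = 21, each participant attending both visits. Assumed: two-sided 0.05, all 21 analysed, normal data with equal SD at both visits, standardised within-visit effect dz (mean on-minus-off effect divided by its between-participant SD) of 0.3, 0.5 or 0.8, and between-visit correlation ρ from 0 to 0.7.

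**Step 1: one visit alone.** The test is a one-sample t with 20 df, critical value 2.086 and noncentrality dz × √21. Power is 0.258 at dz 0.3, 0.587 at 0.5 and 0.936 at 0.8. A control-visit effect of dz 0.3 is therefore missed in 1 − 0.258 = 74% of trials. The 95% CI half-width is 2.086/√21 = 0.455 SD, so an observed control-visit effect of exactly zero is still compatible with about ±0.46 SD.

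**Step 2: the same true effect at both visits, in the predicted direction.** With ρ = 0, P(named target significant, other not) = p(1 − p):

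- dz 0.3: 0.258 × 0.742 = 0.191
- dz 0.5: 0.587 × 0.413 = 0.242
- dz 0.8: 0.936 × 0.064 = 0.060

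Simulation (400,000 trials per cell) extends this to correlated visits:

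| dz | ρ = 0 | ρ = 0.3 | ρ = 0.5 | ρ = 0.7 |
|---|---|---|---|---|
| 0.3 | 0.191 | 0.160 | 0.136 | 0.105 |
| 0.5 | 0.241 | 0.201 | 0.166 | 0.128 |
| 0.8 | 0.060 | 0.054 | 0.048 | 0.038 |

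In every cell a direct paired test between visits rejects in 5.0% of trials, which is 2.5% in the predicted direction. If the common effect runs against the prediction, the pattern supports the hypothesis in at most 0.06% of trials.

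**Step 3: power of the direct contrast.** Suppose the effect is dz 0.5 at one target and 0 at the other. The SD of the between-visit difference is √(2(1 − ρ)) single-visit SDs, so the effective dz is 0.5/√(2(1 − ρ)).

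| ρ | Effective dz | Power | 95% CI half-width of the difference (single-visit SD) |
|---|---|---|---|
| 0 | 0.354 | 0.338 | 0.64 |
| 0.3 | 0.423 | 0.454 | 0.54 |
| 0.5 | 0.500 | 0.587 | 0.46 |
| 0.7 | 0.645 | 0.803 | 0.35 |

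The single-visit test has power 0.587 at dz 0.5, so the contrast matches it at ρ = 0.5 and beats it above that. Adjusting for visit order (19 df, orders split 11/10) gives 0.336, 0.584 and 0.800 at ρ = 0, 0.5 and 0.7.

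**The case against.** The plan is silent rather than contrary. It states no rule that specificity will be judged by comparing significance, and restricting the test to each ROI fixes the region, not the visit. Since each region is the target at one visit and the control at the other, the mixed model could pool visits and carry a target term. That is possible, but the plan does not say it, and where it intends a between-target comparison (perfusion, interbeat intervals) it writes one. Extracting the control region supplies the data for the contrast without specifying it.

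Three limits on the figures stand:

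- They describe a single univariate test such as ROI BOLD. They do not carry over to whole-brain PPI or dual-regression maps, for which the plan states neither threshold nor number of tests.
- They are conditional on a real, equal effect at both visits in the predicted direction. The documents offer no evidence on whether such an effect exists or how large it is, so these are not the plan's error rates.
- Each applies to one hypothesis. For activation, 1a predicts a decrease in the amygdala and 1b an increase in the entorhinal cortex, so a common response of the same sign in both regions would almost never mimic both. This gives partial protection to the pair. It gives none to either hypothesis read alone, nor against a common response of opposite sign in the two regions.

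The power cost is also real, since the between-visit correlation is unknown.

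**Conclusion.** The concern holds. For ROI BOLD, PPI and resting-state connectivity, the written analysis does not test the specificity clause of Hypotheses 1a and 1b; perfusion is the only Hypothesis 1 measure with an explicit between-target comparison. The gap is in the analysis, not the design, because every participant receives both sonications.

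For a single region-level test under the assumptions above, a shared effect of moderate size (dz 0.3 to 0.5) would look target-specific in the predicted direction in about 10% to 24% of trials, against 2.5% for a direct test. At dz 0.8 the excess is small (4% to 6%), and when the shared effect opposes the prediction it vanishes. The argument that a difference between conditions must be tested directly does not depend on these figures and applies equally to the connectivity analyses. The plan should be changed, and nothing in the design prevents it.

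**What to change.** 1. **ROI BOLD.** For each region (right amygdala, left entorhinal cortex), compute each participant's on-minus-off effect at each visit. Analyse the amygdala-visit minus entorhinal-visit difference, with visit order as a centred covariate. An equivalent mixed model would hold target session, on/off, their interaction and a period term, with by-subject random effects for session, on/off and their interaction; that structure may be hard to estimate with 21 participants, so the paired difference is the safer default.
2. **State the hypotheses as contrasts.** For activation, 1a is a more negative on-off effect in the amygdala under amygdala than under entorhinal sonication. 1b is a more positive on-off effect in the entorhinal cortex under entorhinal than under amygdala sonication.
3. **PPI.** Run both seeds at both visits and compare the on-off effects between visits, paired.
4. **Resting state.** Compare post-minus-pre maps between the two sonications, paired, as is planned for perfusion.
5. **Dynamic connectivity.** Say whether condition means on/off or target.
6. **Reporting.** Give each between-target difference with its 95% CI, and do not conclude absence from non-significance. If absence is kept as a claim, set an equivalence margin in advance.
7. **Interpretation.** The section on fMRI and LIFUP administration gives a pulse repetition frequency of 10 Hz for the amygdala and 100 Hz for the entorhinal cortex. The contrast is therefore between two sonication conditions, not between targets alone, and should be described so.

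The cost is revised wording and some extra processing of data the crossover already yields. Power is lower than for a single-visit test when the between-visit correlation is below about 0.5: at dz 0.5 versus 0 it is 0.34 at correlation 0, 0.59 at 0.5 and 0.80 at 0.7, against 0.59. The period term costs almost nothing.

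### The resting-state analysis compares only baseline with post-LIFUP, so the target-specific connectivity claims of Hypotheses 1a and 1b are not tested at rest; the dual-regression maps also need naming

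*Combined protocol and SAP*

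**What the plan says.** Hypotheses 1a and 1b (Data Analysis Plan) each contain a connectivity claim in two parts. Amygdala sonication is expected to lower connectivity between the amygdala and connected regions, and entorhinal sonication to raise it for the entorhinal cortex. Each change is expected not to appear when the other target is sonicated.

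The RS-fMRI section, placed under these hypotheses, first has ICA "extract functional networks from each participant's rs-fMRI". It continues: "Dual-regression analysis will then compare resting state networks between baseline and post-LIFUP to determine the effect of LIFUP on resting state functional connectivity". The model adds three regressors (education, age and sex), and the network changes are then related to emotional reactivity and memory performance. The section contains no term for sonication target. It does not say which spatial maps enter the dual regression.

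The data for a target comparison exist. Under Crossover Design every participant receives both targets at separate visits in counterbalanced order, and under MRI Data Acquisition "we will collect arterial spin labeling and BOLD fMRI both before and after LIFUP".

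**The concern.** A claim that an effect occurs with one target and not the other is a claim about a difference. Testing each target against its own baseline does not test it: one result can reach significance and the other miss it while the two effects are alike. A non-significant change is also not evidence of no change.

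A pre/post contrast in one arm also absorbs whatever else changes between the two scans of a visit, such as time in the scanner, drowsiness or familiarity with the procedure. The plan has no sham condition, so the other target is the only available control for such changes.

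A second, smaller matter sits in the same paragraph. Dual regression regresses a given set of spatial maps into each run. Unless the maps are the same for everyone, a group-level test does not compare like with like.

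**Working it through.** The plan states no figure for this analysis, so there is nothing to reproduce. The check sets the sections side by side and then works out what each contrast estimates.

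| Section | Contrast described | Sonication targets compared? |
|---|---|---|
| Hypotheses 1a, 1b | Change with one target, none with the other | Required |
| RS-fMRI | Baseline versus post-LIFUP | No |
| Stimulation-related fMRI Analysis (PPI, dynamic connectivity) | Stimulation on versus off | Not stated |
| Arterial Spin Labeling | Perfusion change, amygdala versus entorhinal sonication | Yes |
| Physiological Analysis (interbeat intervals) | Target, timepoint and instruction as model factors | Yes, as factors; the interaction is not spelled out |

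**What each contrast estimates.** Let τ_A and τ_E be the true effects of amygdala and entorhinal sonication on a given network measure, and δ the change from time and repeat scanning within a visit, assumed the same on average at both visits.

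- Post minus pre, amygdala visit: D_A = τ_A + δ.
- Post minus pre, entorhinal visit: D_E = τ_E + δ.
- Post minus pre, both visits averaged: (τ_A + τ_E)/2 + δ.
- Paired difference between visits: D_A − D_E = τ_A − τ_E.

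Only the last is free of δ and addresses target specificity. The plan does not say whether the pre/post comparison is made by visit or over both visits. Averaging would be worse: the two hypotheses predict changes of opposite sign, and these would partly cancel in any network that both targets affect.

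**Cost in precision.** Assume D_A and D_E have equal variance σ² and correlation ρ across the 21 participants (Participants), with complete data. Neither σ nor ρ is in the documents.

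- SE of mean D_A = σ/√21.
- SE of mean (D_A − D_E) = σ√(2(1 − ρ))/√21.
- Ratio = √(2(1 − ρ)).

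ρ = 0 gives √2 = 1.41; ρ = 0.25 gives √1.5 = 1.22; ρ = 0.5 gives √1 = 1.00.

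**Template maps.** MRI Analysis states "Functional data will be linearly registered to stereotaxic MNI space", so a common set of maps is feasible. It also states "Analyses will be performed using FSL Version 5.0", but gives no ICA mode. No section mentions a group ICA, external maps, a number of components or which networks will be tested.

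**The case against.** The strongest reply on the target contrast is that resting-state networks are not the main test of these connectivity claims. The hypotheses concern connections of the sonicated region, and the seed-based PPI addresses those directly. That is fair as to emphasis. But the PPI contrast is on versus off, so it does not supply the missing comparison, and the RS-fMRI section gives its own aim as establishing the effect of LIFUP on resting connectivity.

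On the maps, the reply is stronger. A reader might infer that a separate ICA per person is definitely planned, that components will be matched by hand, and that no valid pre/post comparison is possible. The documents support none of these:

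- The ICA sentence names the source of the data and fits a group ICA fed with everyone's scans. Where person-level ICA is meant, the plan says so: "within-subject independent component analysis" appears only for motion-artifact correction. Naming dual regression itself suggests a common set of maps.
- No manual matching step is described anywhere.
- Even with one ICA per person over that person's pooled pre and post runs, the maps would be common to both time points and the within-person contrast would stand. Correspondence across participants is what would be lost, and with it the group test and the association with behaviour.

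What remains on the maps is an ambiguity to clear up.

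**Conclusion.** The missing target contrast is a real gap and holds on any reading of the ICA sentence. Followed as written, the RS-fMRI analysis can show a change over a visit. It cannot show that the change is specific to a target or separate it from time and repeat-scan effects. The size of any resulting error cannot be derived from the documents.

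The conclusion rests on the RS-fMRI section being complete as to its contrasts. The proposed contrast removes δ only if drift within a visit does not depend on the target; counterbalancing the order helps with differences between first and second visits. It also has limits. It compares two active conditions, which differ in pulse repetition frequency as well as in target, and alone it does not say which of them produced a difference. Hence the within-target follow-up.

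The template question is a clarification and does not show the planned comparison to be invalid.

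**What to change.** Amend the RS-fMRI section as follows.

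1. For each participant and visit, form the post-minus-pre dual-regression map. Make the paired amygdala-versus-entorhinal difference in these maps (target by time) the main test, as the ASL section already does for perfusion. Report the within-target pre/post effects as follow-up, with their dependence on time effects noted.
2. If age, sex and education stay in this model, mean-centre them so that the intercept is the average difference between targets.
3. State that one common set of maps is used for every run: either a group ICA over all pre and post runs of both visits, or fixed external maps. Neither choice favours a time point or a target. The group tests and the behavioural association then refer to the same networks in all participants.
4. State the number of components, the networks to be tested and the correction over voxels and networks; the FDR correction in the plan is stated only for ASL.

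The change needs only text and no new scans. Its costs are the precision shown above, somewhat lower than a single pre/post test unless the visits' changes correlate at 0.5 or more, and that common maps do not model networks particular to one individual. If a group ICA was always intended, item 3 alters only the wording.
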